defined as either (1) a specific direction of trunk movement or posture noted during the physical examination or (2) a specific easing factor reported by the patient during the subjective history that alleviates or decreases the patient's pain, with or without the pain having changed location and/or increased the patient's lumbar range of motion (Werneke 2011). A questionnaire including pertinent medical history will be completed (Appendix C). Subjects will complete (1) a Numerical Pain Rating Scale (NPRS) to rate their current, minimum, maximum and average LBP over the last two days (Ferreira-Valente MA 2011) as well as paresthesia signs/symptoms intensity (Appendix D); (2) Body Diagram for indicating location of symptoms (Appendix E); (3) Modified Oswestry low back pain questionnaire (Fritz 2001) (Appendix F); (4) Fear Avoidance Belief Questionnaire (Cleland et al 2008) (Appendix G). A researcher will record subject's height and weight. A Flow chart illustrates study sequence in details (Figure 1).

If the subject meets criteria for inclusion in the study, the subject will complete a familiarization procedure to determine the consistency to reposition themselves in the stadiometer. Subjects able to reposition themselves in the stadiometer with a SD of 1.3mm or less for five consecutive measurements (Stothart et al 2000; Gerke et al 2011; Owens et al 2009) will be included in the study. The digital display will be covered to blind the researcher performing the measurements. The data will be automatically recorded by the stadiometer and manually downloaded to a laptop computer.

At the beginning of data collection, a randomization plan generator

(<http://www.randomization.com>) will assign each subject to one of two interventions: (1) standing *repetitive* trunk extension at a rate of 10 per 45 seconds (Figure 2), repeated five times with 15-second rest breaks; or (2) standing *sustained* trunk extension for 5 x 45 seconds with 15-second rest breaks (Figure 3). Each subject will complete one intervention. The intervention number assigned will be recorded by the subject next to their name to allow blinding of the investigator as to which intervention the subject is assigned to. The subject will undergo the test sequence after a 10-minute period of trunk unloading in a supine posture to ensure spinal height is normalized, head in neutral posture, knees supported over a small bolster pillow, hands placed on the abdomen (Kourtis et al 2004; Magnusson et al 1996a; Gerke et al 2011; Owens et al 2009). The subject will reposition on the stadiometer and spinal height will be measured after a relaxed exhalation (Measurement 1) (Figure 4). The subject then will undergo a five-minute period of loaded upright sitting with a 4.5kg bag secured on each shoulder and spinal height will be measured (Measurement 2) (Figure 5) (Kourtis et al 2004; Owens et al 2009; Gerke et al 2011). As continued spinal height reduction has been demonstrated following loaded sitting, the subject will undergo an additional five minutes sitting without load and spinal height will be measured (Measurement 3) (Kourtis et al 2004; Owens et al 2009; Gerke et al 2011). Inclinometers will be used to take an initial measure of each subject trunk extension prior to intervention. The subject will then undergo one intervention for 5 minutes as previously described, according to the randomization assignment. In order to determine how sustained and repetitive

interventions related in terms of change in spinal height, the time to perform the sustained lumbar posture matches the time necessary to perform the repetitive lumbar extension postures.

The subject will reposition on the stadiometer and spinal height will be measured (Measurement 4). Trunk extension will be measured to determine the strength of correlations between the degree of trunk extension during standing trunk extension posture and spinal height, pain and centralization testing outcomes changes (MacDermid et al 2015). The subject will score their low back and lower extremity symptoms using NPRS (Ferreira-Valente MA 2011), and *map their pain* on a body pain diagram (Appendix E) prior to intervention, immediately after and 2-week following the intervention to determine pain rating and centralization of symptoms (Simmerman et al 2011). The principal investigator will apply a numeric overlay template to the patient's body diagrams to document the most distal pain location scores between 1 and 6 (Appendix I). Higher score will indicate a more distal symptoms' location.

Home instructions

Subjects will be instructed to continue to use their medications, including medications aimed at decreasing their pain, as prescribed by their primary healthcare provider and not to change them during the follow-up two-week period. A sheet including home exercise instructions will be provided to each patient. Instructions will include repetitive or sustained trunk extension based on random group assignment, performed approximately 5 times per day. Each subject will complete a sheet recording home exercise compliance upon arrival in

session 2 (Appendix I).

Session 2

Subjects will complete: (1) a NPRS to rate their current, minimum, maximum and average LBP over the last two days as well as paresthesia signs/symptoms intensity (Appendix D); (2) Body Diagram for indicating location of symptoms (Appendix E) (3) Modified Oswestry low back pain questionnaire (Fritz 2001) (Appendix F); (4) Fear Avoidance Belief Questionnaire (Cleland et al 2008) (Appendix G). Each subject will then complete a familiarization procedure to determine the consistency to reposition themselves in the stadiometer as described in session 1. The subject will undergo a 10-minute period of trunk unloading in a supine posture to ensure spinal height is normalized as described in session 1. The subject will reposition on the stadiometer and spinal height will be measured after a relaxed exhalation (Measurement 1) (Figure 4). The subject then will undergo a five-minute period of loaded upright sitting with a 4.5kg bag secured on each shoulder and spinal height will be measured (Measurement 2) (Figure 5). The subject will then undergo an additional five minutes sitting without load and spinal height will be measured (Measurement 3). Inclinometers will be used to take an initial measure of each subject trunk extension prior to intervention. The subject will then undergo the same intervention as in session 1 for 5 minutes as previously described (standing repetitive trunk extension or standing sustained trunk extension). The subject will reposition on the stadiometer and spinal height will be measured (Measurement 4). Trunk extension will be measured to determine the strength of correlations between the

degree of trunk extension during standing trunk extension posture and spinal height, pain and centralization testing outcomes changes (MacDermid et al 2015). The subjects will then score their low back and lower extremity symptoms using NPRS (Ferreira-Valente MA 2011), and *map their pain* on a body pain diagram (Appendix H).

Investigator Blinding

One investigator will be involved with data collection. The investigator, [name], PT, DPT will carry out inclinometer measurements of lumbar and sacral posture, supervised positioning in the stadiometer and stadiometric measurements. The investigator will be blinded to the intervention (each subject will receive a hidden random number and will perform independently the intervention in a treatment room) and the stadiometric measurements during the experiment. He will also be responsible for assigning subjects to their initial groups, supervising the subjects' positioning in the different standing postures and confirming that a stadiometer reading is recorded on an Excel spreadsheet.

Subjects Compensation

Subjects will receive a one-month free membership to Hill Country Memorial Wellness Center in Fredericksburg, Texas if they consent to participate in the study.

Subjects Charges

There will be no charge for the two physical therapy sessions, including

examination and intervention. Following the two intervention sessions, subjects referred by primary care providers (physicians, chiropractors, nurse practitioners, physician assistants) to physical therapy for LBP will have the choice to receive standard care and be charged for physical therapy intervention.

Confidentiality and data protection

Electronic Transmission of Personally Identifiable Information (PII) and Protected Health Information (PHI) will be followed and computer device has been encrypted (password protected). Excel spreadsheet will be used to store the data. No Personally Identifiable Information will be retained in the Excel spreadsheet where the data will be stored.

Data Analysis

Descriptive and inferential statistics will be used utilizing SPSS 23.0 for Windows (SPSS, Chicago, IL).

1. **Descriptive analyses:** Descriptive statistics including mean, median, mode, standard deviation, minimum and maximum values, frequency counts will be collected for age, height, weight, body mass index, pain, centralization, function (Oswestry Low Back Pain Disability Questionnaire), Fear Avoidance Beliefs Questionnaire, spinal height, and spinal height changes after repetitive and sustained standing trunk extension after a period of spinal loading.
2. **Inferential analyses:** Levene's test and Shapiro-Wilk test of normality will be used to test for variance and distribution of measurements of spinal height,

changes in spinal height, degrees of spinal extension, pain, and function outcomes.

For *experimental hypothesis 1*, a paired-t-test (or Wilcoxon sign-rank test if the data do not meet assumptions for parametric inferential statistics) will be used to assess differences in spinal height, centralization and pain outcomes improvements following sustained and repetitive trunk extension postures.

For *experimental hypothesis 2*, 2 (between subjects - type of trunk extension: sustained vs. repetitive) x 3 (within subjects - time: before, immediately after and 2-week after) mixed ANOVA's will examine differences in (1) spinal height; (2) pain; and (3) function outcomes, as a result of sustained and repetitive standing trunk extension after a period of spinal loading. Post hoc paired t-tests will explore further for significant differences in spinal height, pain and function outcomes between the six conditions.

Experimental hypothesis 3 will be tested with Pearson product-moment correlations to determine the strength of correlations between the degree of trunk extension during standing trunk extension posture and spinal height, pain and function, outcomes changes in patients with LBP.

Spearman's Rank Order correlation will be used to determine the strength of the correlation between centralization and the degree of trunk extension posture in standing.

Alpha level will be set at 0.05 for significance for all tests and Bonferroni corrections performed as needed.

REFERENCES

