APPENDIX H

Body diagram with template for centralization

Date: ____ / ____ /20 Time: ____ am ____ pm Study #: _____

Numeric Overlay Template to the Patient's Body Diagrams

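### The plan describes no masking to time point or arm for the principal investigator's scoring of the body diagrams, so the before/after centralization test is open to reader bias

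*Combined protocol and SAP*

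**What the plan says.** Subjects mark the location of their symptoms on a body diagram "prior to intervention, immediately after and 2-week following the intervention to determine pain rating and centralization of symptoms" (Testing Sequence, Session 1). The same section names the scorer: "The principal investigator will apply a numeric overlay template to the" diagrams. The score runs from 1 to 6 and records the most distal symptom. The section gives the direction as "Higher score will indicate a more distal symptoms' location", so a fall in score is centralization. No second reader, agreement check or procedure for hiding the time point is given.

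The Investigator Blinding section begins "One investigator will be involved with data collection". It blinds that person to the intervention and to the stadiometer readings. Their credentials (PT, DPT) differ from those of the principal investigator on the title page (PT, ScD). The section does not mention the scoring of diagrams.

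Appendix H, titled "Body diagram with template for centralization", has fields for date, time and study number. The Session 2 text cites Appendix H for the diagram marked at the end of that visit. The other diagrams are cited to Appendix E, which is not in the text available for review.

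**The concern.** Research Hypothesis 1 predicts enhanced centralization in both arms, immediately and at two weeks. The Data Analysis section tests it with a paired t-test or Wilcoxon signed-rank test. There is no untreated arm, so a tendency to score later diagrams more proximally goes straight into the before/after difference, and randomization does not remove it. A reader who can tell which diagram came later also knows which direction is expected.

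The plan does protect its main instrument reading: the stadiometer display is covered and the value is recorded automatically. Centralization depends more on a reader, yet no comparable safeguard is described for it.

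**Working it through.** **1. Whether the scorer is masked.** The plan has no figure on this to reproduce, so the check is one of reading. The principal investigator scores. The blinding section covers the data collector, and only for intervention and stadiometer readings. No passage says that diagrams are coded, shuffled or stripped of date before scoring. Masking is therefore not described, either to time point or to arm.

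**2. What is open to judgement.** The patient draws the mark and the zones are fixed. The rule is to record the most distal location, so a mark that plainly covers two zones takes the higher score. Two judgements remain: how the overlay is placed on the drawing, and whether a mark reaches a line at all. Each can move the score by one zone. Below, a borderline diagram means one of these.

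**3. Size, under assumptions.** From the documents: 40 completers and alpha 0.05. Assumed: 20 per arm (the ratio is not stated), two-sided testing (not stated) and no true change. The borderline rate is unknown and is varied.

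*Model A, exact sign test, standing in for the Wilcoxon test.* A share b of diagrams is borderline. A fraction t of these is read toward the hypothesis (before = distal, after = proximal), and the rest at random.

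- Probability that a before diagram is read one zone higher: p1 = b[t + (1 − t)/2]
- Same for an after diagram: p2 = b(1 − t)/2
- Probability of a spurious fall: p1(1 − p2); of a spurious rise: (1 − p1)p2
- Mean spurious shift: p1 − p2 = b·t zones

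With t = 1 there are only falls. The sign test then needs at least 6 of them, since 2 × 0.5^6 = 0.031 but 2 × 0.5^5 = 0.0625. For b = 0.20 the false-positive rate is P(Bin(20, 0.20) ≥ 6) = 19.6%, and for n = 40 it is P(Bin(40, 0.20) ≥ 6) = 83.9%.

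| b | n = 20, t = 0.5 | n = 20, t = 1 | n = 40, t = 0.5 | n = 40, t = 1 |
|---|---|---|---|---|
| 5% | <0.1% | <0.1% | 0.2% | 1.4% |
| 10% | 0.2% | 1.1% | 3.2% | 20.6% |
| 20% | 2.9% | 19.6% | 18.0% | 83.9% |

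With masked reading (t = 0) the rate is at most 0.9% (n = 20) and 2.2% (n = 40) for b up to 30%.

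*Model B, simulated Wilcoxon test (6,000 runs per cell).* Scores also vary at random by one zone, 15% each way. A share of later diagrams is read one zone more proximal. Only claims in the centralizing direction are counted.

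| Share moved | n = 20 | n = 40 |
|---|---|---|
| 0% | 2.6% | 2.5% |
| 5% | 4.4% | 7.1% |
| 10% | 7.7% | 14.8% |
| 20% | 20.4% | 44.7% |

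If 20% of later diagrams are borderline but only half are moved, the 10% row applies: 7.7% and 14.8%.

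The n = 40 columns apply only if the arms are pooled for hypothesis 1. The Data Analysis section does not say so.

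**The case against.** The strongest reply is that little room for bias is left. The patient makes the mark, the zones are fixed, and the most-distal rule acts as a tie-break. A reader might infer that straddling marks have no rule and can freely be read proximally. The documents do not support that: reading a clear straddle proximally would breach the stated rule. This part of the reply stands and narrows the point to overlay placement and marks near a line.

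It is also tempting to say that the scorer sees date and time on every diagram. The header can be confirmed only for Appendix H, cited for the last Session 2 diagram; the Appendix E header cannot be checked. Nor does the plan say that scoring is unmasked. It is silent, and does not say when or in what order scoring is done.

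The largest figures are fragile. A rate near 45% in Model B needs a 20% borderline share, every such diagram read the favourable way, pooled arms, and no floor. Zone 1 cannot be read lower, and eligibility does not require leg symptoms. If half the subjects sat at the floor (an assumption), the 20% row would fall to about 10% (n = 20) and 20% (n = 40). The plan also allows Bonferroni correction as needed.

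Finally, patients know the time point when they draw, and masking the scorer leaves that untouched. This is true. It limits what the fix can achieve, but does not remove the case for it.

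**Conclusion.** The point holds as a gap in the description of outcome assessment: one named scorer, a directional hypothesis, and no stated masking to time point or arm. It bears on the within-group before/after test of hypothesis 1.

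A reader might infer that the comparison of arms under hypothesis 2 is biased as well. Knowing the time point does not by itself favour either arm; that would also require knowing the assignment, and the plan does not say whether the principal investigator knows it.

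All figures on size are assumptions. At 5% the effect is small: at most 1.4% false positives in Model A, and in Model B an excess of 1.8 points (4.4 − 2.6) for n = 20 and 4.6 points (7.1 − 2.5) for n = 40. Near 20%, with consistent reading toward the hypothesis, it could be material: about 20% in one arm of 20 under either model. With half of those marks read that way, it is 2.9% (A) or 7.7% (B). Centralization is one of four dependent variables. This is a minor point, worth acting on because the remedy is cheap.

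**What to change.** Keep the same scorer. Have another member of the team copy the diagrams; cover date, time, session, form label and arm; assign codes; and shuffle the copies across subjects and time points. Link the scores back only after all scoring is complete. Because the text cites two forms (Appendices E and H), use one blank diagram throughout so that the layout does not reveal the visit. State in the protocol how the overlay is aligned and how a mark touching a line is scored. Correct the reference to Appendix I for the template: the template is in Appendix H, and Appendix I is the compliance form.

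The cost is copying and coding: 40 completers × 3 time points = 120 diagrams, or 40 × 4 = 160 if the end-of-Session 2 diagram is also scored. Three investigators are listed, so no new staff are needed. The scoring can be done this way after data collection if the originals are kept. If the diagrams are already masked in practice, one sentence saying so would settle the point. Bias from patients who know the time point when they draw would remain and should be acknowledged in the report.

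### The post-intervention pain score and symptom diagram follow a second trunk-extension test, so the immediate within-subject change can include an extension that is not part of the assigned posture.

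*Combined protocol and SAP*

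**What the plan says.** The Testing Sequence describes two sessions with the same core. After unloading, loaded sitting and unloaded sitting (Measurements 1 to 3), an extension test comes first: "Inclinometers will be used to take an initial measure of each subject trunk extension prior to intervention". The intervention follows: "The subject will then undergo one intervention for 5 minutes as previously described, according to the randomization assignment". Spinal height is then measured (Measurement 4). Next comes a second extension test: "Trunk extension will be measured to determine the strength of correlations between the degree of trunk extension".

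In Session 2 the next step is explicit: "The subjects will then score their low back and lower extremity symptoms using NPRS", together with the body diagram. In Session 1 the rating sentence also comes after the second extension test. It is written as a schedule of three occasions (before, immediately after and two weeks after the intervention) and has no word that fixes its place among the steps.

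Figure 1, as far as its text can be read, puts a second inclinometer measure after Measurement 4. Where it puts the ratings cannot be read.

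Under Data Analysis, hypothesis 1 is tested with paired t-tests or Wilcoxon tests on spinal height, centralization and pain.

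**The concern.** The extension test uses the kind of movement that the trial studies. The inclusion criteria require a directional preference in back extension, which the protocol defines partly by a movement or posture that eases pain. The Background cites rapid changes in pain intensity and location after standing end-range extension. On the protocol's own reasoning, an extension test just before a pain rating cannot be assumed neutral.

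Both arms perform extension and neither is an untreated control. Hypothesis 1 asks whether symptoms improve from before to after within subjects. If the test eases or provokes symptoms, that shift enters the before-to-after difference and is read as an effect of the posture. It does not help that both arms have the same test, because the comparison is not between arms. No later analysis can separate the two contributions, since every subject has the test between intervention and rating.

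**Working it through.** **Order of steps after the intervention**

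| Step | Session 1 | Session 2 |
|---|---|---|
| Measurement 4 | first | first |
| Second inclinometer extension test | next | next |
| Pain score and body diagram | narrated last, but described as immediate | last, stated explicitly |

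Spinal height is read before the test in both sessions; pain and centralization are not.

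**Is the test a separate movement?** It is listed after Measurement 4, so it comes after the intervention has ended and the subject has been repositioned in the stadiometer. The Investigator Blinding section also has subjects perform the intervention independently in a treatment room. A separate extension is therefore the natural reading, though it is an inference.

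**What lies between the before and after ratings?** The first inclinometer test falls after Measurement 3 and before the intervention. Symptoms are rated at intake, and the schedule also lists a rating before the intervention. The plan does not say whether that rating is the intake one or a later one.
- If it precedes the first test, the before-to-after interval contains two test occasions and the intervention.
- If it follows the first test, the interval contains one test occasion and the intervention.

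**Size of the test relative to the intervention.** Inputs from Session 1:
- Repetitive arm: "trunk extension at a rate of 10 per 45 seconds (Figure 2), repeated five times with 15-second rest breaks".
- Sustained arm: "trunk extension for 5 x 45 seconds with 15-second rest breaks".

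The plan's own duration reproduces: 5 × (45 + 15) = 300 s = 5 minutes (285 s if the last rest is dropped). Work time is 5 × 45 = 225 s in each arm. The repetitive arm makes 5 × 10 = 50 extensions and the sustained arm makes 5 holds.

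The number of test extensions (k) and their duration (t) are not given. Assume k = 1 to 3 and t = 2 to 10 s. The added share of work time is k × t / 225:
- k = 1, t = 2 s: 2/225 = 0.9%
- k = 1, t = 4.5 s: 4.5/225 = 2.0%
- k = 3, t = 10 s: 30/225 = 13.3%

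These shares are the same in both arms. They describe exposure only. The documents give nothing that converts exposure into points on the pain scale.

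**The case against.** The strongest objections are these.

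- **Session 1 is the session that matters, and its order is not fixed.** The immediate level of the 2 × 3 design most naturally comes from Session 1. Its rating sentence covers three occasions, so its place in the paragraph cannot settle the order, and read literally it puts the rating straight after the intervention. The explicit order is in Session 2, which also collects ratings on arrival that could supply the two-week value. This stands as a limit on certainty. It does not remove the point: the only order the protocol states outright has the test first, and Session 1 narrates the same order.
- **A test also precedes the intervention.** If the earlier rating follows that test, both ratings come after a test extension. That would soften the problem, but the second test would still lie between the two ratings, and the plan does not say which case applies.
- **The effect may be negligible.** A short test after 225 s of extension work may add little. This stands.

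A reader might go further and infer that the test weighs much more on the sustained arm, and so distorts the comparison in hypothesis 2. By count, one extra extension is 1/5 = 20% of the sustained arm's total and 1/50 = 2% of the repetitive arm's. The documents do not support that inference. It treats a brief test extension as equal to a 45-second hold, whereas the protocol matches the arms on time: "the time to perform the sustained lumbar posture matches the time necessary to perform the repetitive lumbar extension postures". On that scale the share is equal. On time at end range it reverses. Assume 0.5 to 2 s at end range per repetition, the whole of each hold at end range, and one 4.5 s test. The share is then 4.5/225 = 2.0% in the sustained arm, against 4.5/(50 × 2) = 4.5% to 4.5/(50 × 0.5) = 18% in the repetitive arm. The test itself is the same procedure in both arms.

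**Conclusion.** The point holds for the immediate within-subject change in pain and centralization under hypothesis 1. The order is explicit in Session 2 and implied by the narrative in Session 1. As written, those ratings can reflect the assigned posture plus an unassigned extension, in subjects selected for extension preference and without an untreated control.

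The size is unknown and may be near zero. Expressing it in standard errors would need an assumed shift and an assumed standard deviation, and the answer would only restate those assumptions. No differential effect between arms is shown, so hypothesis 2 is not called into question here. Spinal height at Measurement 4 is unaffected.

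The conclusion rests on two readings: that the second inclinometer measure needs its own extension movement, and that Session 1 follows its narrated order. The change is worth making because it costs almost nothing beforehand and analysis cannot recover the separation afterwards.

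**What to change.** In Session 1, Session 2 and Figure 1, place the pain score and body diagram directly after Measurement 4 and before the second inclinometer reading. Write the order explicitly in both sessions, so that it agrees with the description of the rating as immediate.

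State where the pre-intervention rating falls relative to the first inclinometer test, and give the number and duration of test extensions.

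The cost is a reordering of two steps and a few added sentences. The second inclinometer reading comes a minute or two later, and no data are lost.
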